8.7 Adverse events

[figure not shown]
Safety reporting is an integral part of research and should be built into any participant contact and research activities, it is therefore important to record adverse events. Adverse

events can either be because of study conduct (deviation from study documents or processes such as consent), intervention or they could be completely unrelated to the study (missing a course session through physical ill health). These events vary in severity dependent upon the nature of the deviation. It is important to report adverse events particularly those which may have serious or unintended consequences as patterns may be detected on reviewing the records. Adverse events may be reported by the participants, observed or identified by site teams or by researchers when data collecting.

Any serious or other adverse events will be reported according to GCP guidelines see figure 3 (NIHR Decision Tree for Adverse Events Reporting non-CTIMPS) as to whether it is an adverse event that needs documenting at a site level or whether it is a serious event which needs reporting to the CI. We will provide an Adverse Event (AE) log and Serious Adverse Event (SAE) reporting form to all the sites. If an adverse event is detected by a local team, then they will report it to the site PI or delegated person with responsibility, who will log it on the appropriate form and monthly updates will be provided to the research team of any AEs. Serious adverse events must be reported immediately to the Sponsor; it is important to gather as much information about the event as possible. Anyone can report a serious event, and best practice is to err on the side of caution if unsure of whether an adverse event needs reporting.

NIHR | National Institute for Health Research

Decision Tree for Adverse Event Reporting – NON CTIMPS

1

Figure 3. NIHR Decision Tree for Adverse Events Reporting non-CTIMPS

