8.6 Trial conduct

The protocol will be adhered to throughout the study period, any deviations from the protocol will be documented and reported to the CI and sponsor if required.

A serious breach of the protocol will be reported to the sponsor immediately who will determine the seriousness of the breach and whether the REC need informing.

The research team will maintain regular contact with the recruitment sites to address any issues as they arise. The delivery sites will have ongoing supervision throughout the set up and delivery of the intervention to support with any issues relating to the intervention.

The Trial Master File will document all processes and management of the feasibility study including any deviations from the protocol.

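### Section 8.7 mixes protocol deviations and missed course sessions with adverse events, and ties severity to the deviation rather than to the effect on the participant

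*Protocol*

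**What the plan says.** Section 8.7 gives three sources of adverse events. The first two are in one clause: adverse "events can either be because of study conduct (deviation from study documents or processes such as consent), intervention". The third is that "they could be completely unrelated to the study (missing a course session through physical ill health"; this bracket is the only example of an unrelated event. The next sentence sets the basis for grading: "These events vary in severity dependent upon the nature of the deviation".

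On routing, 8.7 refers to GCP guidelines and to the NIHR decision tree for non-CTIMPs (Figure 3). An event found by a local team goes to the site PI or a delegate, "who will log it on the appropriate form and monthly updates will be provided to the research team of any AEs". For serious events, one sentence says that the tree determines "whether it is a serious event which needs reporting to the CI", and a later one says "Serious adverse events must be reported immediately to the Sponsor".

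Section 8.6 has its own rule for deviations. They are documented and go to the CI, and to the sponsor where needed; the Trial Master File also records them. For the grave case, "A serious breach of the protocol will be reported to the sponsor immediately who will determine the seriousness of the breach". Section 8.6.1 names adverse events and protocol deviations as two things in its monitoring list. Section 5.1.2 already collects attendance, with reasons for absence.

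**The concern.** An adverse-event record is useful if each entry is something untoward that happened to a participant, graded by what it did to that person. Section 8.7 departs from this in three ways.

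- A departure from study procedures is listed as a source of adverse events, and the severity sentence then treats the events themselves as deviations.
- The example of an unrelated event is an absence. The untoward occurrence is the illness; the absence is its consequence for attendance.
- Severity is tied to the deviation, which cannot be applied to a fall, an illness or distress during a session.

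Section 8.7 says that events should be recorded because reviewing the records may reveal patterns. Conduct and attendance entries in the same log make such patterns harder to see. Because only one arm attends sessions, part of the added material is one-sided by design. The overlap with 8.6 matters because section 3.5.2 expects that some participants may lose capacity during follow-up, so staff need to know without doubt where a consent deviation goes.

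**Working it through.** The protocol states no adverse-event figure, so there is none to reproduce. The check sets the sections side by side and adds a count of where missed-session entries could arise.

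**1. Is a deviation treated as an adverse event?** Taken alone, the first clause can be read as a list of causes. The severity sentence does not fit that reading: it refers back to all the events just listed, including intervention-related and unrelated ones, and grades them by a deviation that most of them would not involve. Section 8.6.1 keeps adverse events and deviations apart, which suggests that the merging in 8.7 is a drafting fault and not a choice.

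**2. Who can have a missed-session entry?** Inputs: three sites, with 12 intervention and 6 usual-care participants per site (section 3.6), and six sessions (section 4.1).

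- Intervention participants: 3 × 12 = 36
- Usual-care participants: 3 × 6 = 18
- Intervention person-sessions that could be missed: 36 × 6 = 216
- Usual-care person-sessions that could be missed: 18 × 0 = 0

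Good adherence would not remove the exposure. Completion means at least 4 of 6 sessions (section 2.3), so if all 36 participants just met it, 36 × 2 = 72 sessions would still have been missed. This is a ceiling under full completion, not a forecast. The protocol gives no expected rate of missed sessions and no share due to ill health, so an expected number of entries cannot be calculated.

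**3. Is the information needed in the log?** No. Section 5.1.2 records attendance and the reasons for absence. A missed-session entry under 8.7 would duplicate that record.

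**4. Where does a consent deviation go?**

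- Section 8.6, ordinary deviation: documented; to the CI, and to the sponsor where needed; recorded in the Trial Master File; no time limit stated.
- Section 8.6, serious breach: to the sponsor at once.
- Section 8.7, adverse event not classed as serious: to the site PI or delegate; adverse-event log; monthly update to the research team.
- Section 8.7, serious adverse event: the CI in one sentence, the Sponsor at once in another.

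The same deviation fits both sections. They differ in recipient, form and timing, and neither says which governs or that both apply.

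**5. Serious events within 8.7.** The two sentences name two recipients. Only the Sponsor sentence carries a timing, and nothing says whether the site informs both or whether one passes the report to the other.

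**The case against.** The strongest reply is that the first clause of 8.7 lists causes, which is ordinary relatedness language, and that classification rests on GCP guidelines and Figure 3, whose content is not visible here and may contain a proper definition. The same paragraph also stresses events with serious or unintended consequences, so effect on the person is not ignored. Part of this stands: the cause reading is available for the first clause. It does not rescue the severity sentence or the missed-session example. The text describes the decision tree as a means of sorting events into site-level documentation or serious reporting, not as defining what an event is. If the figure does hold a definition, the prose beside it still needs to agree with it.

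A reader might infer several stronger points that the protocol does not support.

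- *That the log fails to measure harm.* Intervention-related and unrelated events are still logged, and serious ones have their own form. The fault is mixing, not absence.
- *That 8.6 and 8.7 conflict.* Both can be followed, and serious matters reach the Sponsor at once under each.
- *That a deviation would be reported weeks late.* Section 8.6 sets no time limit for ordinary deviations, so there is no baseline for a delay.
- *That a particular number of spurious entries would arise.* This needs rates of absence and illness that the protocol does not give.
- *That the CI and Sponsor sentences contradict each other.* They name two recipients and do not exclude one another.

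It is also fair to say that adverse-event counts are not among the feasibility outcomes (section 2.3), the planned descriptive analyses (6.1) or the progression criteria (6.1.1). No stated result or progression decision changes.

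**Conclusion.** The point holds as a fault in a stated rule. Section 8.7 mixes deviations and absences with adverse events and grades severity on the wrong basis. Followed literally, it produces a log that combines harm with conduct and attendance entries. The missed-session part could arise only among the 36 intervention participants, over 216 person-sessions, and never among the 18 in usual care. The one-sidedness follows from the design and needs no assumption beyond full recruitment and allocation as planned; the number of entries remains unknown. Illness itself can of course be recorded in either arm, so the zero for usual care applies to missed sessions only.

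The reporting routes overlap and need to be reconciled. The consequence is limited to the quality of the safety record and its use for detecting patterns. That is enough to justify the change, given how little it costs.

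**What to change.** Reword section 8.7 as follows.

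- Define an adverse event as an untoward physical or psychological occurrence in a participant, in either arm, with severity and seriousness judged by its effect on the person. Remove the severity sentence that refers to the deviation.
- Replace the missed-session example: the illness is the event to record, and the absence stays in the attendance record under 5.1.2.
- Take deviations out of 8.7 and handle them under 8.6 only. If a deviation causes harm, log that harm under 8.7, with a cross-reference between the two sections.
- Reconcile the CI and Sponsor sentences into one serious-event reporting chain that states who tells whom and when.
- Check that Figure 3 agrees with the revised wording.

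The cost is one paragraph and the adverse-event log template. No additional data or staff are needed.

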9 TRIAL MANAGEMENT

The CI of the project will have overall responsibility for the project and have oversight of the different components of the study. The project will be managed from the University of York.

9.1 Project management group (PGM)

The Project Management Group consists of all the co-applicants on the project alongside delivery partners and staff from the 3 recruitment sites. The group consists of a mix of experts by experience, dementia care practitioners and university research staff. It numbers 14 members and meets quarterly online. The group inputs into all aspects of the ongoing set up and delivery of the project, including development of study documentation, monitoring progress, discussing any issues as they arise and inputting into reports and dissemination.

9.2 Study steering committee

The study steering committee is likely to total 8-10 members in total with a mix of skills and knowledge from backgrounds such as the Department for Health and Social Care, dementia advocacy organisations and members with lived experience. This group will have an independent chair and will meet twice a year online. Its remit will be to inform the trial and maximise impact and dissemination of knowledge.

9.3 Sponsor and funding

University of York are the sponsors for this feasibility trial and National Institute for Health and Care Research (NIHR) Three Schools: Dementia Research Programme the funding body (Reference NIHR 356285).

10 DISSEMINATION

The research will produce new knowledge on the inclusive implementation of a manualised version of GL and the feasibility of a trial including diverse populations. Pathways to impact will be targeted at operational and strategic levels, with a view to both informing current use of the intervention and developing plans for further research. A strategic impact plan will be developed co-productively with our advisers and collaborators, but is likely to include:

- 1. Three in-person knowledge exchange events** in the delivery sites, with one additional online event to maximise opportunities for impact nationally. These will be advertised using

existing university platforms and the applicant team's wider networks, including through the Study Steering Committee, three-strand advisory network and site-based research partners. These events will share findings and seek views on potential effects, challenges and next steps.

2. Production of targeted resources to support effective and consistent delivery of GL, including dissemination of the manual and training pack to ensure best practice.

3. A suite of wider strategic, practice and public facing resources to share research findings across the health and social care landscape, with a consideration of relevance for service provision at local and national policy levels. These resources will be developed in partnership with our Study Steering Committee and three-strand advisory network to ensure relevance and inclusivity. They could include commissioner briefings, practice guidance, summaries for DHSC/NHS England and written, infographic or audio-visual resources for people with lived experience and family carers. Resources will be hosted online by the University of York for ongoing accessibility and publicised by university media teams and dementia networks.

4. Presentations to maximise impact through practice and commissioning networks including ICB E&E committees, Communities of Practice, MSNAP, NHS England, Journal of Dementia Care, Future NHS and research dissemination initiatives such as Making Research Count and the Curiosity Partnership. The research team has extensive contacts within these networks.

10.1 Authorship eligibility guidelines

Data arising from the study will be owned by the Sponsor, The University of York. The researchers will aim to publish a research article in a peer-reviewed academic journal.

